9.2 Patient Disposition

All patients who provided informed consent will be included in a summary of patient accountability.

The following categories will be summarised by cohort/treatment subgroup and overall as follows:

- Patients screened
- Screening failures
- Patients eligible to receive dose
- Patients dosed
- Patients completing 72 weeks treatment period
 - Patients not enrolled in optional extension treatment period
 - Patients enrolled in the optional extension treatment period
 - Patients ongoing in optional extension treatment period

- Patients discontinuing optional extension treatment period (including reasons for treatment discontinuation)
- Patients discontinuing 72 weeks treatment period early (including reasons for treatment discontinuation)
- Patients who have undergone biliary diversion surgery
- Patients who have undergone liver transplantation
- Patients who have been listed for liver transplantation

Additionally, analysis populations will be summarised overall and by region ([Appendix C](#)).

9.3 Protocol Deviations

All protocol deviations will be reviewed at the final protocol deviations review meeting before final database lock, through clinical input provided by the Sponsor, using the following sources of information:

- Protocol deviation logs, provided by ICON Clinical, Pharmacovigilance, Medical, and Data Management.

Important protocol deviations that are likely to impact the efficacy and safety will be identified by the study team during the manual review at the data review meeting prior to DB lock. The list of important protocol deviations will be finalized after the data review meeting. The number of patients with important protocol deviations (overall and by deviation) will be summarised by cohort/treatment subgroup and overall.

9.4 Demographic and Baseline Characteristics

9.4.1 Demographic Characteristics

Age, height, weight, and BMI at baseline and other demographic variables, e.g. age category (<6 months, 6 months to 5 years, 6 to 12 years, 13 to 18 years, and >18 years), sex, race, ethnicity, country, region ([Appendix C](#)) will be summarised descriptively by cohort/treatment subgroup and overall.

Demographics data for Cohort 1 will be obtained from Study A4250-005, as appropriate.

9.4.2 Baseline and Disease Characteristics

The following disease characteristics will be summarised by cohort/treatment subgroup and overall: years since PFIC diagnosis; type of PFIC; Bile Salt Export Pump (BSEP) subtype for PFIC 2 Patients and BSEP genotype; presence of significant pruritus per Investigator report; at least 1 serum bile acid level $>100 \mu\text{mol/L}$ within 6 months before Screening visit; serum bile acid category; reasons for discontinuation of historical PFIC-related investigational medications; baseline Z-score; Use of UDCA or/and Rifampicin and diagnostic genetic laboratory test as well as Child-Pugh classification and hepatic impairment classification per NCI Organ Dysfunction Working Group.

Child-Pugh classification: mild (Class A), moderate (Class B), or severe hepatic impairment (Class C) is based on the FDA Guidance for Pharmacokinetics in Patients with Impaired Hepatic Function. Determination of the classification is made based on medical review of baseline laboratory data and medical history.

Hepatic impairment will also be classified per the NCI Organ Dysfunction Working Group classification as mild, moderate or severe (Mansfield et al. 2016)⁶. Both the Child-Pugh and NCI classification will be included in the baseline characteristics and both will be applied in the subgroup analysis based on hepatic impairment status.

The following continuous parameters will also be summarized: estimated glomerular filtration rate (eGFR); baseline Z-score (weight, height, BMI and mid-arm circumference); and baseline values of alanine aminotransferase (ALT); aspartate aminotransferase (AST); gamma-glutamyl transferase (GGT); total bilirubin; alkaline phosphatase; INR; and vitamins A, E, and 25 hydroxy D.

eGFR will be calculated based on the modified/bedside Schwartz equation. For patients <18 year of age, Bedside Schwartz Equation will be used:

$$\text{GFR (mL/min/1.73 m}^2\text{)} = (36.2 \times \text{Height in cm}) / \text{Creatinine in } \mu\text{mol/L}$$

For patients ≥ 18 years, the isotope dilution mass spectrometry (IDMS)-traceable Modification of Diet in Renal Disease (MDRD) Study equation will be used:

⁶ Aaron S. Mansfield, Michelle A. Rudek, Diana Vulih, Gary L. Smith, Pamela Jo Harris, and S. Percy Ivy (2016). "The effect of hepatic impairment on outcomes in phase 1 clinical trials in cancer subjects".

GFR (mL/min/1.73 m²) = 175 × (Creatinine in µmol/L/88.4)^{-1.154} × (Age)^{-0.203} × (0.742 if female) × (1.212 if African American)

The average of three repeat measurements of mid-arm circumference will be calculated for the analyses.

If length instead of height is measured for patients, height of the patients will be calculated from length by using the formula:

Height (cm) = Length (cm) – 0.7 cm.

A listing will present demographic and baseline characteristics by patient. In addition, an individual listing of liver biopsy results, including historical liver biopsy results for patients in Cohort 2, will be produced.

The results of pathologic variants identified for ATP8B1, ABCB11, ABCB4, or other genes (such as NR1H4, TJP2, DCDC2, CLDN1, MYO5B) will be listed for all patients.

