3.3.7 PELD/MELD Score

The paediatric end-stage liver disease (PELD) score was calculated for children under 12 years of age. For children 12 years of age or older, the model for end-stage liver disease (MELD) score was calculated.

For calculation of the PELD/MELD score³ laboratory parameters will be converted in following units:

- Total bilirubin in mg/dL
- Albumin in g/dL
- Creatinine in mg/dL

PELD score = $4.80 * \ln(\text{total bilirubin}) + 18.57 * \ln(\text{INR}) - 6.87 * \ln(\text{albumin}) + 4.36$ (if patient <1 year: scores for patients listed for liver transplantation before the patient's first birthday continue to include the value assigned for age (<1 year) until the patient reaches the age of 24 months) + 6.67 (if the patient has growth failure [< -2 StdDev])

Laboratory values <1.0 were set to 1.0 for the calculation of the PELD score.

MELD score = $9.57 * \ln(\text{creatinine}) + 3.78 * \ln(\text{total bilirubin}) + 11.2 * \ln(\text{INR}) + 6.43$

Laboratory values <1.0 were set to 1.0 and serum creatinine values >4.0 mg/dL (equivalent of 353.6 µmol/L) were set to 4.0 for calculation of the MELD score.

If a patient went from 11 years of age to 12 between the beginning and end of study, both PELD and MELD scores were to be calculated at the first visit after the 12th birthday and move to MELD score.

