4.2 Secondary Efficacy Endpoints

The secondary efficacy endpoints include the following:

- **EU and RoW:** Proportion of positive pruritus assessments at the patient level over the 72-week treatment period using the Albireo ObsRO instrument.
- **US:** Change from baseline in fasting serum bile acids after 72 weeks of treatment.
- **All Regions:**

- Change from baseline in serum bile acids at Weeks 4, 12, 22, 24, 36, 46, 48, 60, 70, 72, 76 and all visits (every 16 weeks) during the optional extension period.
- Proportion of individual assessments meeting the definition of a positive pruritus assessment at the patient level using the Albireo ObsRO instrument from Weeks 0-4, Weeks 0-12, Weeks 0-22, Weeks 0-24, Weeks 0-36, Weeks 0-46, Weeks 0-48, Weeks 0-60, and Weeks 0-70, and the proportion of positive pruritus assessments at each 4--week interval between Visit 1/Screening and Visit 5/Week 24, then by each visit between Visit 5/Week 24 and Visit 12/Week 76.
- Proportion of individual AM assessments meeting the definition of a positive pruritus assessment at the patient level using the Albireo ObsRO instrument from Weeks 0-4, Weeks 0-12, Weeks 0-22, Weeks 0-24, Weeks 0-36, Weeks 0-46, Weeks 0-48, Weeks 0-60, Weeks 0-70, and Weeks 0-72, and the proportion of positive pruritus assessments at each 4-week interval between Visit 1/Screening and Visit 5/Week 24, then by each visit between Visit 5/Week 24 and Visit 12/Week 76.
- Proportion of individual PM assessments meeting the definition of a positive pruritus assessment at the patient level using the Albireo ObsRO instrument from Weeks 0-4, Weeks 0-12, Weeks 0-22, Weeks 0-24, Weeks 0-36, Weeks 0-46, Weeks 0-48, Weeks 0-60, Weeks 0-70, and Weeks 0-72, and the proportion of positive pruritus assessments at each 4-week interval between Visit 1/Screening and Visit 5/Week 24, then by each visit between Visit 5/Week 24 and Visit 12/Week 76.
- Number of patients undergoing biliary diversion surgery or liver transplantation. These parameters will be evaluated separately and together at Weeks 24, 48, 72 and all visits (every 16 weeks) during the optional extension period.
- Change in growth from baseline to Weeks 12, 24, 36, 48, 60, 72 and all visits (every 16 weeks) during the optional extension period after initiation of odevixibat treatment, defined as the linear growth deficit (height/length

for age, weight for age, and BMI) compared to a standard growth curve (Z-score, StdDev from the fiftieth percentile, P50).

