9.6.4 Analyses of Secondary Endpoints

All secondary analyses will primarily be summarised descriptively based on the FAS, unless otherwise specified.

The change in secondary endpoints such as serum bile acids, growth, APRI score, Fib-4 score, PELD/MELD will be summarised by visit using descriptive statistics.

❖ Growth

Change in growth (height/length for age, weight for age, mid-arm circumference for age, and BMI for age) will be analysed by using the 1-sample t-test or the Wilcoxon signed

rank test, as appropriate at the end of the 72-week treatment period based on the average of the values at Weeks 70 and 72. In addition, change in growth will also be displayed using graphical presentations. Baseline 1 and 2, defined in the table of derived variables in [Appendix A](#), will be used to calculate change from baseline for data analysis. Baseline 1 will only be used for patients in Cohort 1 who were on odevixibat in Study A4250-005.

The analysis of growth data for height/length, weight, and BMI will be based on calculated values using the software or methods from the Centers for Disease Control and Prevention (CDC) website for patients with age ≥ 2 years old and from the WHO website for patients with age < 2 years old^{7,8}. The analysis of growth data for mid-arm circumference will be based on calculated values for 2 months to 18 years for U.S. Children⁹. CRF collected growth data will be listed.

❖ Serum Bile Acids

For serum bile acids assessments, if a patient has assessments at Weeks 70 and 72, then the average of the 2 assessment values at Weeks 70 and 72 will be used for data analysis. This handling will also be applied to Weeks 22 and 24, and Weeks 46 and 48.

❖ Proportion of Positive Pruritus

The proportion of individual assessments meeting the definition of a positive pruritus assessment at the patient level on the Albireo ObsRO instrument from Weeks 0-4, Weeks 0-12, Weeks 0-22, Weeks 0-24, Weeks 0-36, Weeks 0-46, Weeks 0-48, Weeks 0-60, Weeks 0-70, or the proportion of positive pruritus assessments at each 4-week interval between Visit 1/Screening and Visit 5/Week 24, then by each visit between Visit 5/Week 24 to Visit 12/Week 76 will be summarised descriptively as for the primary analysis for the US. Similar summaries will be provided based on AM scores as well as PM scores.

⁷ <https://www.cdc.gov/nccdphp/dnpao/growthcharts/resources/sas.htm> following CDC's method

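### The 0.7 cm length-to-height conversion has no age limit, so on a literal reading it lowers height/length-for-age Z and raises BMI in children under 2, who are scored by the WHO method

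*SAP*

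**What the plan says.** Section 9.4.2 of the SAP gives the rule: "If length instead of height is measured for patients, height of the patients will be calculated from length by using the formula", and then "Height (cm) = Length (cm) – 0.7 cm". It has no age condition and does not say which derived variables use the result. The same section lists among the baseline variables "baseline Z-score (weight, height, BMI and mid-arm circumference").

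Section 9.6.4 sets the growth reference by age. The CDC and WHO methods are divided as follows: "website for patients with age ≥ 2 years old and from the WHO website for patients with age < 2 years old". The variables analysed there are "Change in growth (height/length for age, weight for age, mid-arm circumference for age, and BMI for age"), with a one-sample t-test or signed rank test at the end of the 72-week period. Section 4.2 makes change in growth a secondary endpoint.

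BMI is weight over height squared (section 3.3.3 and Appendix A). Section 9.4.1 plans an age category below 6 months, so infants are expected.

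**The concern.** By applying the formula at all, the SAP accepts that a child's length and standing height differ by 0.7 cm. The value scored must then be of the same kind as the measure behind the reference. Children measured lying down are mainly the youngest, and those under 2 go to the WHO method. If 0.7 cm is taken off a true length and the result is scored against a length reference, the child appears shorter than he or she is. BMI computed from the reduced value is too high.

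The error need not cancel in a change score. A child who is lying at baseline and standing at Week 72 has a distorted baseline and an undistorted end value. The study has no concurrent control to absorb such an artefact, and for height it runs in the direction of benefit.

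**Working it through.** The SAP states no figure on this point, so there is nothing to reproduce.

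**Inputs**
- Conversion of −0.7 cm at any age (SAP 9.4.2).
- WHO method below 2 years, CDC method from 2 years (SAP 9.6.4).
- BMI = weight/height² (SAP 3.3.3, Appendix A).
- Week 72 target day 504 (SAP Appendix B, Table 4).
- SD of length-for-age under age 2: not in the SAP; assumed 2.0 to 3.5 cm.
- Share of patients who cross age 2 and change measuring position: not in the SAP; assumed 5% to 30%.
- The under-2 reference rests on length: not stated in the SAP; inferred because infants, including the planned group below 6 months, cannot stand.

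**Height/length Z under age 2.** Shift = −0.7/SD.
- SD 2.0 cm: −0.7/2.0 = −0.35
- SD 2.5 cm: −0.7/2.5 = −0.28
- SD 3.0 cm: −0.7/3.0 = −0.23
- SD 3.5 cm: −0.7/3.5 = −0.20

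**BMI.** Inflation = (L/(L − 0.7))² − 1.
- L = 55 cm: (55/54.3)² − 1 = 2.6%
- L = 70 cm: (70/69.3)² − 1 = 2.0%
- L = 85 cm: (85/84.3)² − 1 = 1.7%

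**Who crosses age 2 by Week 72.** 504 days/30.44 = 16.6 months, and 24 − 16.6 = 7.4. Children aged about 7.4 to under 24 months at first dose therefore reach age 2 by then. Those measured lying at baseline and standing at Week 72 lose the bias between visits: height Z gains 0.20 to 0.35 spuriously, and BMI falls spuriously.

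**Who stays under 2.** The bias is present at both visits and mostly cancels. It shrinks only as the SD grows: for SD 2.2 cm rising to 3.0 cm, 0.7/2.2 − 0.7/3.0 = 0.318 − 0.233 = +0.08 Z.

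**Overall mean change in height Z.** Share × individual gain: 0.05 × 0.20 = +0.01 at the low end and 0.30 × 0.35 = 0.105, about +0.10, at the high end.

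**Weight and mid-arm circumference Z.** Neither uses height, so there is no effect.

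**The case against.** The strongest reply is that the SAP never says the converted height, rather than the measured length, goes into the WHO calculation. The formula sits among baseline derivations, shortly after an eGFR equation that needs height in cm. It may exist only to supply a height where a formula asks for one. Growth scoring has its own section, which names the variable height/length for age; that wording would be redundant if every length had already become a height.

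This reading is possible, but nowhere stated. Section 9.4.2 is the only operative instruction and it applies whenever length is measured. Even if the conversion served only eGFR and BMI, BMI-for-age under age 2 would still be computed from a reduced length.

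It is also fair that the SAP does not describe the WHO reference and only links to it. That the reference is length-based is an inference from the age of the children, though a firm one for those who cannot stand.

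Other parts of the reply stand and limit the point:
- A reader might infer that all of the infants' Z-scores are biased low. Only height/length is; BMI moves the other way, and weight and mid-arm circumference do not move.
- A reader might infer a false gain for every child who passes age 2. That requires lying measurement at baseline, standing measurement at Week 72, and scoring of the converted value. The same children also change from WHO to CDC, which adds a shift of unknown sign and size, so their net change cannot be put down to the 0.7 cm alone.
- A reader might infer a spurious PELD improvement, because that score adds "6.67 (if the patient has growth failure [< -2 StdDev"]). Section 3.3.7 names no growth measure for this term and does not refer to the conversion, so the effect is conditional on the term using the same height Z.
- Growth is one of many secondary endpoints in a study without formal hypothesis testing (section 5), and the growth data collected on the CRF will be listed, so raw values can be checked.

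**Conclusion.** The point holds in a limited form. As written, the conversion gives a wrong result below age 2: height/length-for-age Z too low by about 0.20 to 0.35, and BMI too high by about 2% (2.0% at 70 cm, 1.7% at 85 cm). This rests on an assumed SD of 2.0 to 3.5 cm, on a length-based under-2 reference and, for the height Z, on the converted value being the one scored.

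The spurious change at Week 72 is confined to children who cross age 2 and change measuring position. Its effect on the overall mean is about +0.01 to +0.10 Z under the assumed 5% to 30%, and the true share is unknown. The documents do not establish a bias in all growth Z-scores, a false gain in every child who passes age 2, or any effect on PELD. The rule should be corrected because the test is one-sample and uncontrolled, and because two programmers could follow the present text and obtain different Z-scores for the same infant.

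**What to change.** In section 9.4.2, limit the subtraction of 0.7 cm to length measured at age 2 or over. In section 9.6.4, state that below age 2 measured length is used unchanged for the WHO length-for-age and BMI-for-age scores. State which value enters BMI, and which growth measure and value enter the PELD growth-failure term in section 3.3.7. Add a sensitivity analysis of change in growth that either scores both visits of children who cross age 2 on one reference or excludes those children.

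The cost is a few sentences in the SAP, one condition in the derivation program and one additional table. No new data are needed.

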9.4.3 Medical and Surgical History

The frequencies and percentages of patients with reported medical and surgical history will be presented by system organ class (SOC) and preferred term (PT). Medical and surgical history will be coded using Medical Dictionary for Regulatory Activities (MedDRA), Version 26.0 or later. The summary table will be sorted alphabetically by SOC and PT. Medical and surgical history will also be listed.

For patients with BRIC, a flare/cholestatic episode can be self-reported or clinically assessed based on medical history. The frequency, duration, and severity of flares within the last 6 months at a minimum, and within the last 5 years, other clinical signs and symptoms during a cholestatic episode/flare including nausea, vomiting and pruritus followed by jaundice, fatigue, weight loss, malaise, steatorrhoea, night blindness, increased bilirubin and alkaline phosphatase levels and increased INR, ALT, AST and GGT, if possible, will be listed.

9.4.4 Prior and Concomitant Medications

Prior and concomitant medications used in this study will be coded using the March 2023 version or later of the World Health Organisation (WHO) Drug Global Dictionary.

Prior medication: A medication taken by a patient within 3 months before the first dose date of study drug with a recorded medication stop date before the first dose date of study drug is a prior medication. This will not include historical PFIC-related investigational medications collected separately on CRFs.

Concomitant medication: A medication taken by a patient the day on or after the first dose date of study drug or a medication with a start date before the first dose date of study drug without a recorded stop date before the first dose date of study drug is a concomitant medication.

As patients in Cohort 1 enter the study directly from Study A4250-005, the summary of prior medications is provided only for Cohort 2. Concomitant medication use during the study will be summarised descriptively using frequency tables by Anatomical Therapeutic Chemical (ATC) Class 4 and PT by cohort/treatment subgroup and overall for the FAS. ATC class and PT will be presented alphabetically. All prior and concomitant medications will be listed. Details for imputing missing or partial start and/or stop dates of non-study medications are located in [Appendix D](#).

9.5 Extent of Exposure

9.5.1 Treatment Duration

Exposure will be summarised with descriptive statistics (n, mean, StdDev, minimum, median, and maximum) and presented by cohort/treatment subgroup and overall.

For Cohort 2 patients who dose escalate from 40 µg/kg/day to 120 µg/kg/day, exposure at each dose and overall will be calculated.

Categorical summaries of treatment duration will also be provided. Study drug exposure will be derived as follows:

Duration of exposure (in weeks) = (date of last study drug intake – date of first study drug intake + 1)/7.

Investigators are allowed to interrupt the study drug to allow for the resolution of AEs, if necessary. Drug interruptions will not be considered when calculating treatment duration.

9.5.2 Treatment Compliance

Treatment compliance will be assessed by maintaining adequate study drug dispensing records. Treatment compliance over the treatment period will be calculated using 2 sources of data.

9.5.2.1 Source Data from CRFs

Treatment compliance = $100 \times [(number\ of\ capsules\ dispensed - number\ of\ capsules\ returned)/number\ of\ capsules\ that\ should\ have\ been\ taken]$.

The number of capsules that should have been taken is calculated as the number of days that patient was in the treatment period (exposure as above) multiplied by the number of prescribed capsules to be taken (based on patient's body weight, Protocol Table 3) during the treatment period. The total number of capsules actually taken is the total number of capsules recorded as taken based on the CRF (number of capsules dispensed minus returned) summed over the treatment period. If the number of capsules returned is confirmed as missing and the study drug is confirmed has not been returned, the derivation will not be done.

9.5.2.2 Source Data from eDiary

Treatment compliance = $100 \times (total\ number\ of\ capsules\ taken/total\ number\ of\ capsules\ planned\ to\ be\ taken)$. The number of capsules planned to be taken will be estimated based on patient's body weight per Protocol Table 3. The compliance rate based on eDiary data will be calculated during the first 24 weeks only.

The calculated compliance rates will be summarised and the one based on CRFs will be considered the primary compliance rate. The compliance rates reported by visit on the CRFs also will be summarised.

Descriptive summary statistics will be used to summarise study drug compliance by cohort and overall. The number and percentage of patients with a compliance <80%, between 80% and 120%, and >120% will also be presented.

